holds promise for the study and treatment of neurological disorders. Yet, there is a limited understanding of the effects of rTMS on brain and behavior. The efficacy of present rTMS therapy, in which the brain state is uncontrolled during stimulation, is highly variable. This is not surprising given that neural activity patterns at the time of stimulation can impact the effects of rTMS on brain and behavior outcomes. Leaving the brain state unconstrained during stimulation likely leads to aftereffects that can spread to remote (unintended) brain areas rather than targeting specific neuronal subpopulations and functional networks underlying the behavior of interest. The past few years have been directed at developing protocols that systematically control behavior to manipulate dynamic patterns of neural activity during stimulation so that the stimulation-induced effects are more specific. Even so, a mechanistic framework to guide and optimize future applications of therapeutic rTMS is still lacking. There is a critical need for a basic understanding of how rTMS interacts with dynamic patterns of neural activity to induce persistent changes in neural circuits underlying motor control. This gap in knowledge precludes the development of biologically-based rTMS protocols in basic neuroscience and clinical practice.

Significance:

The rationale for this project is that it will allow us to identify the mechanisms associated with improvements in motor function to target for future clinical applications of rTMS.

Our overall **objectives** in the current study are to:

1. Elucidate the neural mechanism by which rTMS paired with a motor task leads to improvements in motor function.
2. Develop more targeted network modulatory rTMS interventions to enhance motor function.

*Aim-specific objectives described in detail below under “research design”

The **specific aims / hypotheses** in the current study are:

[figure not shown]
1. Demonstrate improvement in action performance by manipulating the behavioral state during PPC stimulation. Based on preliminary data, our working hypothesis is that action performance will improve after PPC stimulation and will improve even more after stimulation during grasp performance.

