2. Demonstrate modulation of neurophysiological aftereffects of PPC stimulation by manipulating behavioral state. Based on preliminary data, our working hypothesis is that motor excitability will increase after PPC stimulation and will increase even more after stimulation during grasp performance.
3. Assess the relationship between brain connectivity, plasticity and behavior in response to the behavioral state during brain stimulation. Our working hypothesis is that constraining the behavioral state during PPC stimulation will induce greater changes in functionally specific parietal-motor pathways within the targeted cortical grasping network, as compared to PPC stimulation alone. Exploratory analyses will examine correlations between changes in action performance, plasticity, and functional connectivity.

RESEARCH DESIGN:

Participants will be asked to participate in up to nine sessions – the sessions will take place in either the TMS laboratory in the Kinesiology Building ([name]) or the Functional MRI Laboratory located in the Bonisteel building ([name]). The visit schedule is as follows:

- Session 1: Screening + behavioral & neurophysiological measures (~2 hours)
- Session 2: fMRI (~1 hour)
- Session 3: TMS (~30 min)
- Session 4: TMS (~30 min)
- Session 5: TMS (~30 min)
- Session 6: TMS + behavioral & neurophysiological measures (~3 hours)
- Session 7: TMS + fMRI (~1 hour)
- Session 8*: fMRI (~1 hour)
- Session 9*: behavioral & neurophysiological measures (~1 hours)

*Option to complete visits 8 and 9 on the same day

Subjects will be randomly assigned to one of three rTMS intervention groups in a 1:1:1 ratio. As depicted in **Figure 1**, subjects will complete fMRI scans, electrophysiological measures with TMS, and behavioral measures before and after five consecutive rTMS sessions. The first fMRI assessment session on visit 2, without rTMS, will obtain baseline measurements of hand motor function, electrophysiology with TMS, and fMRI-derived connectivity (providing the PPC target

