The objective of Aim 1 is to show improvement of manual dexterity after strengthening functional specific neural pathways with iTBS PPC + Grasp. To examine the effects of five-day stimulation and behavioral state on action performance, we will use a repeated measures model to test the hypothesis that the time to complete the 9-HPT will be reduced (i.e.,

performance improvement) after TBS PPC alone relative to iTBS Vertex + Grasp, and that the performance improvement will be greater for iTBS PPC + Grasp compared to iTBS PPC alone. We will use two sided tests, because it also is possible that performance may worsen, either with stimulation alone, or when combined with subjects performing the grasp task. It would be critical to know for future therapeutic purposes, for example, that manual dexterity was degraded by combining rTMS with a motor task. We also will perform an exploratory assessment on mean force and rectified EMG for a finger abduction task inspired by Bunday and Perez²⁷ to estimate persistent effects of stimulation on voluntary motor output. In addition to testing questions about performance, we also will examine relationships between action performance and the electrophysiology and fMRI measures from Aims 2 and 3, testing important questions around this mechanism.

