The objective of Aim 2 is to determine inter-cortical interactions from PPC to motor plasticity. Descriptive statistics will be used to explore the distribution, central tendency, and variation of each measurement. Normality for each variable will be checked using a Shapiro-Wilks test, and appropriate transformations (i.e., log) will be used when necessary. To examine state-dependency modulation of rTMS-induced effects on motor plasticity, we will contrast the size of MEPs elicited in the resting hand muscle by TMS over M1 following iTBS PPC + Grasp with those following iTBS PPC alone. We will test the following: the size of MEPs evoked by TMS will be greater for iTBS PPC alone relative to iTBS Vertex + Grasp, and whether the MEPs will be greater for iTBS PPC + Grasp, compared to iTBS PPC alone. Because the MEP amplitude can be highly variable from trial-to-trial within the same subject,²⁸ we will collect 24 MEPs, the optimal number of single-pulse TMS trials required for the reliable assessment of motor cortical excitability.^{29,30} In addition, to avoid the confounding influence of diurnal variations in levels of cortisol on the induction of cortical plasticity,³¹ all experiments will occur at the same time of day. Based on prior work,³² it is possible that subjects with more excitable motor systems will have greater behavioral improvements after rTMS. We, will therefore perform additional analyses examining the relations of inter-individual differences in MEP amplitude, magnitude of the plasticity effects in the motor system,³³ and the rTMS-induced behavioral effects.³⁴ Knowledge of this variability will provide insight into how interventions can be personalized and optimized for stroke recovery.

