The third aim of this study is to assess the relationship between brain connectivity, plasticity and behavior in response to the behavioral state during brain stimulation. Exploratory analyses will test for correlations between the three measures, to provide a richer picture of iTBS effects. In order to assess functional connectivity between disparate brain regions, we will calculate correlations between the time series of disparate brain regions. For each seeded region of interest, we will produce a whole brain map of Pearson's r values that can subsequently be transformed using Fisher's r-to-z transform to allow for standard statistical testing. Regions that display a high degree of correlation ($p < 0.05$, corrected for multiple comparisons) are assumed to be "functionally connected" with that node. To examine the effect of iTBS on functional connectivity, we will directly contrast the MRI sessions following iTBS PPC + Grasp with iTBS PPC alone and iTBS Vertex + Grasp using our previous methods.³⁵ Exploratory analyses will search for regions outside the a priori defined network that change

with stimulation to develop a comprehensive picture of how iTBS interacts with brain networks. All data from our fMRI scans also will be publicly posted at Open fMRI (<http://openfmri.org/>) to allow other researchers to validate our results and perform supplemental analyses.

MEASUREMENTS

The neurophysiological measurements for the current study are:

- **Motor threshold** in hand muscles as defined as the lowest TMS intensity needed to generate MEPs of >50 μ V in at least 5 of 10 trials when the muscle is completely relaxed (resting MT; RMT) and the minimum intensity required to produce MEPs of $\geq 200\mu$ V in at least 5 of 10 trials while the participant maintains 20% maximum contraction in the targeted hand muscle (active MT; AMT).
- **MEP amplitude** will be measured with 1 mV TMS intensity. A fixed stimulation intensity to elicit a ~ 1 mV MEP will be determined for each participant before testing to examine the changes in MEP after the different plasticity induction protocols. Twenty-four MEPs will be acquired at each time point. Stimuli will be applied every 5 s.

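### The exploratory correlations between behaviour, MEP and connectivity changes specify no arm term, so a correlation pooled over the three arms can reflect arm differences and be read as mechanism

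*Combined protocol and SAP*

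**What the plan says.** Participants are "randomly assigned to one of three rTMS intervention groups in a 1:1:1 ratio" (Research design): iTBS PPC + Grasp, iTBS PPC alone, and iTBS Vertex + Grasp.

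The linking analyses appear in several places:

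- Specific aims / hypotheses, item 3: "Exploratory analyses will examine correlations between changes in action performance, plasticity, and functional connectivity".
- Detailed objectives, Aim 3: "Exploratory analyses will test for correlations between the three measures, to provide a richer picture of iTBS effects".
- Detailed objectives, Aim 1, which gives the purpose: "examine relationships between action performance and the electrophysiology and fMRI measures from Aims 2 and 3, testing important questions around this mechanism".
- Detailed objectives, Aim 2, which adds further analyses of individual differences in MEP amplitude, plasticity effects and behavioural effects.

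None of these names a model, an arm covariate, stratification by arm or a within-arm estimate. Arm does appear where each outcome is compared between groups, but not where outcomes are related to one another. The Statistical design section covers sample size only.

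On arm order, Aim 1 expects PPC alone to improve 9-HPT time relative to Vertex + Grasp, and expects that "the performance improvement will be greater for iTBS PPC + Grasp compared to iTBS PPC alone". Aim 2 states the same order for MEP size. For connectivity, item 3 of the aims expects more change when the behavioural state is constrained during PPC stimulation than with PPC stimulation alone. It does not place Vertex + Grasp.

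**The concern.** A correlation across all participants mixes two things: the association between individuals within an arm, and the association between arm means. Only the first tells us whether people whose MEP or connectivity changed more also improved more. The second repeats the randomised group comparisons. If two measures shift in the same arm order, the pooled coefficient departs from zero even when the individual-level association is nil.

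The plan hypothesises such a shared order for behaviour and MEP. The first study objective is "Elucidate the neural mechanism by which rTMS paired with a motor task leads to improvements in motor function", and the Aim 1 text links the associations to mechanism. The more clearly the group comparisons for Aims 1 and 2 succeed, the more likely a pooled 9-HPT/MEP correlation is to reach significance for a reason unrelated to an individual-level link.

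**Working it through.** **Inputs from the plan.** Three arms, 1:1:1; required N of 54, hence 54/3 = 18 per arm; alpha 0.05; planning effect η² = 0.11. Two-sided testing is stated for Aim 1 and assumed here for the correlations.

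**The plan's own figure.** With f² = 0.11/0.89 = 0.1236, three groups, three time points, and noncentrality f²(N − 3)(3 − 1), N = 54 gives 0.1236 × 51 × 2 = 12.61 on 4 and 102 degrees of freedom, power 0.804. N = 51 gives 0.775. So 54 reproduces under these settings, which the plan does not itself state. The sample size is not in question here.

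**Assumptions.** The documents do not give the share of change-score variance explained by arm. I use 11% as an illustration, borrowing the size of 0.11; in the plan that figure is a stimulation-by-session interaction from another study. I show 5% and 20% as an assumed range. With equally spaced arm means a step d apart (in within-arm SDs), (2/3)d² = η²/(1 − η²), so 5%, 11% and 20% correspond to steps of 0.28, 0.43 and 0.61 SD. Correlations are signed so that positive means improvement (shorter 9-HPT time) accompanies increase.

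**Expected pooled correlation.** With zero within-arm association and equal arms, all covariance lies between arms, so

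r = c × √(η²_X × η²_Y),

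where c is the correlation between the two sets of arm means. For 9-HPT with MEP under the stated order and equal steps, c = 1. At 11% each, r = √(0.11 × 0.11) = 0.11.

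**False-positive rates for 9-HPT with MEP** (simulated, 18 per arm, zero within-arm link):

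| Variance explained by arm | Expected r | Pooled | Arm as factor |
|---|---|---|---|
| 5% and 5% | 0.05 | about 6.5% | about 5% |
| 11% and 11% | 0.11 | about 12% | about 5% |
| 11% and 20% | 0.15 | about 19% | about 5% |
| 20% and 20% | 0.20 | about 31% | about 5% |

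**The two connectivity pairs.** Here c depends on the unstated position of Vertex + Grasp. If connectivity follows the same equally spaced order, c = 1. If Vertex + Grasp equals PPC alone, c = 0.87; if it lies midway between PPC alone and PPC + Grasp, c = 0.5; if it equals PPC + Grasp, c = 0. At 11% each, the pooled rate for a single connectivity pair is then about 12%, 11%, 6.5% and 5% respectively.

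**At least one false link among three pairs:**

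| Vertex + Grasp on connectivity | 11% each | 11% (9-HPT), 20%, 20% |
|---|---|---|
| Same order as behaviour and MEP | 32% | 53% |
| Equal to PPC alone | 30% | 47% |
| Midway | 23% | 33% |
| Equal to PPC + Grasp | 21% | 27% |

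The right comparator is about 14%, not 5%: three tests at 5% give 1 − 0.95³ = 14%, and that is what the arm-adjusted analysis returns in every row.

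**Cost of adjustment.** The pooled test has 54 − 2 = 52 degrees of freedom, with critical |r| 0.268. With arm as a factor there are 50, with critical |r| 0.273.

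**The case against.** Five points can be made for the plan.

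- **It does not say the arms will be pooled.** This stands. The text is silent on arm, and Aim 3 is framed around behavioural state, which partly defines the arms, so a within-arm reading is open. A reader might infer a commitment to a pooled analysis; the documents support only that the handling of arm is unspecified. Taken literally, though, a correlation between changes with no further model is a pooled one.
- **Only two of the three measures have a stated common order.** This stands. A reader might infer that connectivity is hypothesised to follow the order of behaviour and MEP. The aims rank it only for PPC + Grasp over PPC alone, so the 32% and 53% rates are upper ends of a range.
- **The correlations are labelled exploratory.** This stands. No primary or secondary outcome is an association between two of these measures, and Aim 3's working hypothesis is tested by direct contrasts between arms. It would be too strong to say that Aim 3 or the first objective rests on the correlations. The label does not settle the interpretation, because the Aim 1 text gives the associations a mechanistic purpose.
- **The inflation is modest at the only effect size the plan gives.** This stands for a single test: about 12% against 5%. The plan does expect behavioural effects to be the most subtle, so larger arm effects on MEP or connectivity are plausible, but it gives no sizes for them.
- **Adjustment for arm would not prove mechanism.** Correct. MEP and connectivity changes are not themselves randomised, so a within-arm association remains observational.

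The Aim 2 question whether people with more excitable motor systems benefit more is separate. If excitability is measured at baseline, randomisation makes it independent of arm in expectation and this artefact does not arise.

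**Conclusion.** The concern holds in a limited form. The plan leaves arm out of its exploratory correlations between change scores while giving them a mechanistic purpose, and a correlation pooled over arms can be non-zero with no individual-level link. For 9-HPT with MEP, where the common order is stated, the false-positive rate is about 12% at 11% of variance each, with an assumed range from about 6.5% (5% each) to about 31% (20% each), against 5% with arm in the model. Across three pairs it is about 21% to 32% at 11% each, against 14% adjusted.

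These figures assume 54 analysed participants in equal arms, equally spaced arm means for 9-HPT and MEP, and no within-arm association. They require arm effects on both measures with aligned patterns; where the patterns are unrelated there is no inflation. The randomised comparisons and all listed outcomes are untouched. This is an inexpensive improvement that should be made, not a flaw in the trial's main analyses.

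**What to change.** State in the analysis plan that each association between changes in 9-HPT, MEP and connectivity is estimated with arm as a factor, by partial correlation or regression, and reported with its 95% confidence interval. Base any statement about mechanism on this within-arm estimate and describe it as associational.

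The cost is a sentence or two of text and two degrees of freedom, which moves the critical |r| at N = 54 from 0.268 to 0.273. No new data are needed.

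An arm-by-slope term, asking whether the association differs between arms, is optional and should be labelled descriptive. It takes two more degrees of freedom and has little power: by Fisher's z, the standard error of a difference between two arms of 18 is √(2/15) = 0.365, so a true 0.5 against 0 (0.549 on the z scale) is detected with about 32% power.

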- **Object directed grasping:** Subjects will perform a precision grip with the right hand towards either a small or large target object positioned in front of them. The illumination of an LED (green or red) will instruct the subject to plan a precision grip towards either a small or large target object positioned in front of them. After ~1 second, the LED will extinguish and cue subjects to execute the intended object-directed hand action. The presentation of the visual stimuli will be synchronized with the iTBS stimulation, which will occur 800ms before the onset of every "GO" cue in order to modulate cortical activity during both the planning and execution phase of the action.

Outcome measures for the current study are:

Primary Outcome Measures:

1. Percentage change in the time to complete the nine-hole peg test (9-HPT) to immediate post-intervention. 9-hole peg test is a manual dexterity measure, estimated as the time required to complete the task (seconds). Time Frame: Baseline and immediate post-intervention.
2. Percentage change in amplitude of motor evoked potential (MEP) to immediate post-intervention. Motor cortical excitability is measured by electromyography using MEPs elicited by TMS Time Frame: Baseline and immediate post-intervention.
3. Change from baseline functional connectivity to PPC stimulation target within the cortical grasping network to immediate post-intervention. Resting-state connectivity of low frequency BOLD fluctuations for a seed at the PPC. Time Frame: Baseline and immediate post-intervention.
4. Change from baseline Blood Oxygen Level-Dependent (BOLD) activation, voxelwise in the cortical grasp network to immediate post-intervention. Parietal-frontal cortical grasping network defined by BOLD change while subject performs the precision force-tracking task. Time Frame: Baseline and immediate post-intervention.

Secondary Outcome Measures:

1. Percentage change in the time to complete the nine-hole peg test (9-HPT) to 1-week post-intervention. 9-hole peg test is a manual dexterity measure, estimated as the time required to complete the task (seconds). Time Frame: Baseline and 7-15 days post-intervention.
2. Percentage change in amplitude of motor evoked potential (MEP) to 1-week post-intervention. Motor cortical excitability is measured by electromyography using MEPs elicited by TMS. Time Frame: Baseline and 7-15 days post-intervention.

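### Aim 3's imaging arm comparison does not say how the baseline scan enters, none is written for task BOLD, and baseline adjustment would be more precise than either reading of the text

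*Combined protocol and SAP*

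**What the plan says.** The design is parallel-group (Research Design): "Subjects will be randomly assigned to one of three rTMS intervention groups in a 1:1:1 ratio". Scans are planned on both sides of the intervention: "subjects will complete fMRI scans, electrophysiological measures with TMS, and behavioral measures before and after five consecutive rTMS sessions". The visit schedule puts the baseline scan at Session 2, the immediate post-intervention scan at Session 7 and the later scan at Session 8.

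The two imaging primaries are worded as changes. Primary outcome 3 is "Change from baseline functional connectivity to PPC stimulation target within the cortical grasping network to immediate post-intervention". Primary outcome 4 is "Change from baseline Blood Oxygen Level-Dependent (BOLD) activation, voxelwise in the cortical grasp network to immediate post-intervention". Secondary outcomes 3 and 4 repeat them at 7-15 days.

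The arm comparison is in Detailed objectives, Aim 3. Its sentence opens "To examine the effect of iTBS on functional connectivity" and continues "we will directly contrast the MRI sessions following iTBS PPC + Grasp with iTBS PPC alone and iTBS Vertex + Grasp". It ends by deferring to the team's previous methods, with a citation to a cerebellar theta-burst connectivity study. It names no baseline scan, change score, covariate or arm-by-session term. Neither Aim 3 nor Statistical Design, which deals only with sample size, gives an arm comparison for task BOLD.

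Aim 1 is more explicit about the peg test: "we will use a repeated measures model to test the hypothesis that the time to complete the 9-HPT will be reduced".

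**The concern.** Three analyses fit the text: compare post-intervention scans between arms, compare change scores, or compare post-intervention scans adjusted for baseline. On the same data they give different estimates, and the post-only and change-score estimates differ by exactly the observed baseline difference between the arms. Read literally, the Aim 3 sentence is the first of these, while the outcome definition suggests the second.

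The contrast is between different people, so stable individual differences in connectivity count as noise unless the baseline scan is used to remove them. With about 18 per arm, chance baseline imbalance is not negligible. At stake are the precision of two of the four primary outcomes and the freedom to choose the estimator after the scans have been seen. For task BOLD there is not even a sentence to interpret.

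**Working it through.** **Inputs from the documents.** Three arms at 1:1:1 (Research Design). Required sample 54, from eta squared 0.11, alpha 0.05 and power 0.8 (Statistical Design), so 54 / 3 = 18 per arm. Two-sided testing is stated for Aim 1 ("We will use two sided tests") and assumed here for imaging.

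**The plan's own figure.** The 54 reproduces as a 3-group by 3-session interaction: f² = 0.11 / 0.89 = 0.1236; noncentrality = 0.1236 × (54 − 3) × 2 = 12.6; df 4 and 2 × 51 = 102; power 0.804. At 53 participants power is 0.794. The plan does not state the G*Power test or options, so this layout is inferred from the fact that it returns 54. The calculation was made for action performance, not imaging; it is used here only for the 18 per arm.

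**Inputs not in the documents.** The baseline-to-post correlation (rho) and the imaging effect size. I show rho at 0.3, 0.5 and 0.7, and fix the effect so that the post-only contrast has power 0.80.

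**Formulas.** Outcome SD is 1 at both times. The contrast is between two of three arms, two-sided 0.05, non-central t with noncentrality (d / SD) × √(18/2) = 3d / SD.

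- Post-only: SD = 1, error df 51. Power 0.80 needs d = 0.952 (noncentrality 2.856).
- Change score: SD = √(2(1 − rho)), error df 51.
- Baseline-adjusted: SD = √(1 − rho²), error df 50.

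| rho | Change-score variance | Adjusted variance | Post-only power | Change-score power | Adjusted power |
|---|---|---|---|---|---|
| 0.3 | 1.40 | 0.91 | 0.80 | 0.658 | 0.835 |
| 0.5 | 1.00 | 0.75 | 0.80 | 0.800 | 0.899 |
| 0.7 | 0.60 | 0.51 | 0.80 | 0.951 | 0.975 |

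Variances are relative to post-only. Example at rho 0.5: adjusted SD = √0.75 = 0.866, noncentrality 2.856 / 0.866 = 3.298, power 0.899. The adjusted column ignores a small penalty for estimating the slope beyond the one degree of freedom, so it is slightly generous.

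**A smaller effect.** At d = 0.8, treating the two arms alone (df 34, or 33 adjusted), post-only power is 0.65, adjusted power 0.69, 0.77 and 0.90, and change-score power 0.50, 0.65 and 0.85 at the same three correlations. The ordering is unchanged.

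**Chance imbalance.** The standard error of a baseline difference between two arms is √(2/18) = 0.33 SD. A difference beyond 0.5 SD in either direction is 0.5 / 0.333 = 1.5 standard errors, probability about 0.13 for a given pair. Given an imbalance of 0.5 SD and rho = 0.5, a post-only estimate shifts by 0.5 × 0.5 = 0.25 SD in the direction of the imbalance, and a change score by (0.5 − 1) × 0.5 = −0.25 SD. Adjustment removes both shifts on average.

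**Bias.** Averaged over randomisation the baseline difference is zero, so all three contrasts have the same expected value. A simulation with a true difference of 0.8 averaged 0.80 for both the post-only and the change-score contrast.

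**The case against.** The strongest objection is that the plan may already use the baseline scan. The sentence defers to an earlier method that cannot be inspected here. The outcome definitions speak of change, the Aim 3 hypothesis speaks of greater changes, and the sentence that follows looks for regions that change with stimulation. A contrast of change scores is at least as natural a reading as a post-only one. This stands: a reader might infer that the baseline scan is left out, but the documents support only that its role is not stated. It does not remove the point, because a change score is also less precise than adjustment (0.66 against 0.84 at rho 0.3).

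A reader might also infer that a post-only contrast fails to test change, or is biased. Under 1:1:1 randomisation it is not: the expected arm difference is the same, and chance imbalance is sampling error that the test's alpha already covers. The loss is one of precision. What a post-only contrast cannot give is the change within an arm.

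Nor does a post-only contrast lose power against every alternative. Against a plain change score it loses only when rho exceeds 0.5; at 0.3 it does better (0.80 against 0.66). Against adjustment the loss at rho 0.3 is only 3.5 points.

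Finally, the calculation is for one scalar measure at an uncorrected 0.05, with an effect chosen to make post-only power 0.80. Primary outcome 4 is voxelwise, and Aim 3 describes whole-brain maps with corrected thresholds. The figures therefore rank the three analyses and say nothing about this trial's actual imaging power. That limit is accepted.

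**Conclusion.** The point holds in this form: for primary outcome 3 the plan does not state how the baseline scan enters the arm comparison, and for primary outcome 4 no arm comparison is written. These are two separate gaps, since the Aim 3 sentence is confined to connectivity. Adjusting for the baseline scan already planned is more precise than either reading of the text.

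Under the assumptions above, the gain over post-only is about 4, 10 and 18 points of power at rho 0.3, 0.5 and 0.7 (0.835, 0.899 and 0.975 less 0.80). The gain over a change score is about 18, 10 and 2 points (0.835 − 0.658, 0.899 − 0.800, 0.975 − 0.951). Which comparison matters depends on what the sponsor intended and on a correlation that the documents do not give. If rho is low and post-only was meant, the gain in precision is small and the main benefit is a fixed estimator.

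The documents do not support reading this as a biased analysis or as a fault in the sample size of 54, which was set on action performance. The change should be made because it is nearly free and settles the analysis of two primary outcomes in advance.

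**What to change.** In Detailed objectives, Aim 3, replace the contrast sentence with a model statement along these lines:

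- For primary outcomes 3 and 4, arms are compared on the post-intervention value (Fisher-z connectivity from the PPC seed within the grasping network; task activation in the grasp network), with arm as factor and the participant's own baseline value of the same measure as covariate.
- For network summaries the covariate is the baseline network mean. For voxelwise maps it is the baseline value at the same voxel.
- The same model is used for the matching 7-15 day outcomes (secondary outcomes 3 and 4).
- Two arm contrasts are named: PPC + Grasp against PPC alone, and PPC alone against Vertex + Grasp. These match Aims 1 and 2. The current Aim 3 sentence can be read as setting PPC + Grasp against Vertex + Grasp; if the sponsor wants that contrast instead, the plan should say so. The model is the same.

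The cost is one degree of freedom per model (51 to 50 with 54 participants) and slightly more set-up for a voxel-specific covariate. No extra scan, visit or participant is needed.
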